11.0 Vulnerable Populations*

No Vulnerable patients will be enrolled in this study.

12.0 Local Number of Subjects

All 10 patients will be enrolled at this facility by the primary surgeon. This is a modest number of subjects to allow us to properly evaluate the feasibility of evaluating subscapularis tendon perfusion by two different takedown techniques in shoulder arthroplasty.

13.0 Recruitment Methods

Participation in this research requires informed consent according to Institutional Review Board (IRB) guidelines and a signed IRB-approved Consent Form as the means of documenting this understanding.

Patients, 18 years of age or older who present to DHMC with shoulder arthritis who meet the inclusion criteria will be considered for enrollment. This study requests a partial waiver

PROTOCOL TITLE: Pilot feasibility study of dynamic contrast-enhanced fluorescence imaging to guide total shoulder arthroplasty approach

of HIPAA for recruitment purposes. The partial waiver would allow for the surgeon to share with the research coordinator the patient name, sex, MRN number, age, underlying conditions as well as type and location of injury. There is an adequate plan to protect identifiers from improper use and disclosure as information will only be used by study team members to determine whether a patient may be eligible. Information will only be communicated and stored using D-HH approved secure platforms. Information is only being used to determine if a patient is eligible for the study, for recruitment purposes. Once approached, if a patient is not interested, information will be destroyed. Protected health information will not be re-used or disclosed for another purpose. It will only be used for recruitment. This research could not practically be done without a partial waiver of HIPAA. This information is needed for recruitment. Patients will sign a full HIPAA Authorization when consenting to the study.

Upon identification, study personnel will screen the patient for eligibility and if eligible, the study will be introduced to the patient by a member of their care team. If the patient agrees, a member of the study team will approach them for informed consent. Screening will occur from the daily orthopaedic patient clinic schedule for the principle investigator. Study participants will be enrolled in the clinic setting prior to their surgical procedure.

To obtain informed consent, study personnel will adhere to the following procedures: (1) present study information in a manner that is understandable to the patient; (2) discuss the study with the patient and answer any questions; (3) allow the patient an opportunity to discuss participation with their family; (4) confirm that the patient understands the risks and benefits of participating in the study and that their participation is voluntary; and (5) complete the consent process and obtain signatures from the patient and research team. The process of obtaining and documenting informed consent will be completed in accordance with Good Clinical Practice.

Potential recruits are instructed that their participation is completely voluntary and that their medical care will not be altered in any way should they elect not to participate at any time prior to surgery.

No advertisements or other promotional material will be used. No finder fees or recruitment incentives will be offered.

There will be no honorarium or payment in association with this study.

14.0 Withdrawal of Subjects*

Participants will be removed from the protocol if:

- 1) Concern for subscapularis tendon tear or insufficiency occurs.
- 2) The subject withdraws consent.

PROTOCOL TITLE: Pilot feasibility study of dynamic contrast-enhanced fluorescence imaging to guide total shoulder arthroplasty approach

- 3) The subject has an occurrence of a significant clinical event that precludes proceeding with surgery.
- 4) Imaging cannot be completed for any reason

If a participant is withdrawn from the protocol, the PI will mark the data of this subject as "withdrawn" and will add a detailed explanation about the cause of withdrawal in the database.

For subjects who withdraw after the intraoperative imaging, but prior to their first post operative appointment, we will follow-up to see if they still complete their clinical follow up at the 1-month interval, and provide them an opportunity to report any adverse events. We will acquire their follow up results to include these subjects in the statistical analysis portion that only involves the intraoperative image data and infection status.

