1.0 Study Summary

Study Title	Pilot feasibility study of dynamic contrast-enhanced fluorescence imaging to guide total shoulder arthroplasty approach
Study Design	Cross sectional study
Primary Objective	To evaluate the feasibility of open wide-field imaging of indocyanine green ingress and egress during total shoulder arthroplasty.
Secondary Objective(s)	To characterize the relationship between tissue perfusion measured with DCE-FI and different approaches and techniques used in total shoulder arthroplasty.
Research Intervention(s)/Investigational Agent(s)	Assignment of research participants to subscapularis peel or tenotomy techniques utilized during total shoulder arthroplasty surgical approach. Indocyanine Green (ICG) indicated for soft-tissue perfusion assessment
IND/IDE #	N/A
Study Population	Patients who are undergoing open surgery for shoulder arthroplasty
Sample Size	10 patients
Study Duration for individual participants	4-6 weeks
Study Specific Abbreviations/Definitions	AIF: arterial input function CDC: Centers for Disease Control and Prevention CRF: Case Report Forms DCE-FA: Dynamic Contrast Enhanced Fluorescence Arthroscopy DCE-FI: Dynamic Contrast Enhanced Fluorescence Imaging DoD: US Department of Defense D-HH: Dartmouth-Hitchcock Health DHMC: Dartmouth Hitchcock Medical Center FI: fluorescence imaging GCP: Good Clinical Practice GFR: glomerular filtration rate HRPP: Human Research Protection Program ICG: Indocyanine Green NSF: nephrogenic sclerosing fibrosis PDD: Pulse Dye Densitometer ROI: Region of interest SSI: Surgical Site Infection

PROTOCOL TITLE: Pilot feasibility study of dynamic contrast-enhanced fluorescence imaging to guide total shoulder arthroplasty approach

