4.0 Study Endpoints*

Primary end point:

To assess the technology and its ability to see blood supply in the subscapularis tendon before takedown and after employed repair. The benchmark for this is the rise and fall of fluorescence signal approximately 10-40 seconds after injection. Given our experience in DCE-FI for bone fractures, it will be more or less self-evident whether the DCE-FA signal is sufficient for further analysis.

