A Pulse dye densometer (PDD; in-house developed), similar to a pulse oximetry probe, which is used clinically both in the operating room, in inpatients as well as outpatients to assess oxygen saturation. This is completely non-invasive. In the context of this study the pulse dye densometer collects data on the ICG injection parameters so that the kinetic curves can be normalized to injection-related differences. The PDD will be placed on the patient's finger to acquire an arterial blood input function during ICG injection.

After the subscapularis tendon is visualized during the surgical approach, 0.1 mg/kg ICG will be injected intravenously. Video rate ICG fluorescence images will be acquired 20 seconds before and 4 minutes after ICG injection. This process will be repeated towards the end of the procedure after the subscapularis is repaired, but prior to skin closure.

ICG will be administered by an anesthetist in the operating room. Patients are under the care and observation of the anesthesia and surgical teams during this time. Postoperatively, patients are transferred to the Post-Anesthesia Care Unit (PACU) where they are monitored

PROTOCOL TITLE: Pilot feasibility study of dynamic contrast-enhanced fluorescence imaging to guide total shoulder arthroplasty approach

continuously by nursing staff supervised by anesthesiologists. During this entire time vital signs (including temperature, pulse, respiratory rate and blood pressure) are collected as standard of care. All clinical data will be reviewed for adverse events for a period of 30 minutes post-injection.

Day of surgery Procedures	Pre-Infusion	0-30 minutes post-infusion
Pulse	X	X
Blood Pressure	X	X
Temperature	X	X
Respiratory Rate	X	X
Adverse Events		X

Study patients will be seen per usual protocol for wound assessment and general health assessment after their shoulder arthroplasty at approximately 4 weeks post operatively.

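### Section 14.0 withdraws participants whose imaging cannot be completed, without saying that failures of the imaging process still count against the primary feasibility aim

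*Protocol*

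**What the plan says.** The primary objective in section 1.0 is "To evaluate the feasibility of open wide-field imaging of indocyanine green ingress and egress during total shoulder arthroplasty". Section 4.0 states the primary endpoint as "To assess the technology and its ability to see blood supply in the subscapularis tendon before takedown and after employed repair", and adds: "The benchmark for this is the rise and fall of fluorescence signal approximately 10-40 seconds after injection". Section 12.0 justifies the 10 patients on the same ground, as enough to "properly evaluate the feasibility of evaluating subscapularis tendon perfusion by two different takedown techniques".

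Section 6.0 describes two acquisitions per patient. For the first: "Video rate ICG fluorescence images will be acquired 20 seconds before and 4 minutes after ICG injection". For the second: "This process will be repeated towards the end of the procedure after the subscapularis is repaired, but prior to skin closure".

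Section 14.0 begins "Participants will be removed from the protocol if" and gives four grounds. The first three are a suspected tendon tear or insufficiency, withdrawal of consent, and a clinical event that prevents surgery. The fourth is "Imaging cannot be completed for any reason". The investigator flags the data of such a participant as withdrawn and writes the cause into the database. The section then says that participants who leave once operative imaging is done, but before their first clinic visit, are kept in the part of the analysis that uses image data and infection status. It says nothing similar for participants removed under the fourth ground.

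**The concern.** In a study of whether imaging can be done, a failure to obtain the images because of the imaging process is a negative result on the main question. The fourth ground treats that event as a withdrawal. It also pools failures of the device, dye delivery, field of view or theatre workflow with causes that say nothing about the technology.

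If the removed cases are also left out of the feasibility result, that result describes only participants in whom imaging worked well enough to be completed. What is at stake is how favourable the pilot looks to those who use it to plan later work.

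**Working it through.** **Inputs.** N = 10 (sections 1.0, 5.3 and 12.0). Two acquisitions per patient (section 6.0). Benchmark at about 10-40 seconds after injection (section 4.0). The protocol gives no feasibility proportion, pass mark, imaging failure rate, power or precision target, so there is no figure of its own to reproduce. All counts and rates below are assumptions for illustration.

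**The passages side by side.** Section 4.0 needs perfusion to be seen at both time points. A patient in whom either acquisition fails for an imaging-process reason has therefore not met the endpoint. Section 14.0 removes that same patient. Consent withdrawal and events that prevent surgery have their own grounds, so failure of the imaging process is a large part of what the fourth ground adds.

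**Effect on the result.** Let m be the number of incomplete cases in which the benchmark was not captured at both time points, and s the number of completed cases without signal.

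- Failures counted: (10 - m - s)/10
- Failures left out: (10 - m - s)/(10 - m)

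The 95% intervals are exact (Clopper-Pearson). When all n cases succeed the lower limit is 0.025^(1/n); for n = 8 this is 0.631. With s = 0:

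| m | Counted | Left out |
|---|---|---|
| 0 | 10/10 = 100% (69-100%) | the same |
| 1 | 9/10 = 90% (55.5-99.7%) | 9/9 = 100% (66-100%) |
| 2 | 8/10 = 80% (44-97%) | 8/8 = 100% (63-100%) |
| 3 | 7/10 = 70% (35-93%) | 7/7 = 100% (59-100%) |

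**Direction.** The numerators are equal, and the second denominator is never larger. Over all 65 combinations with m = 0 to 9 and m + s at most 10, the left-out figure rises in 45, is equal in 20 (m = 0, or no successes) and falls in none.

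**Limit on direction.** An acquisition stopped after 40 seconds but before 4 minutes may already show the benchmark. Suppose one such case, one completed case without signal and eight completed cases with signal. Judged on the benchmark the result is 9/10 = 90.0%; with the truncated case removed it is 8/9 = 88.9%. Removing that kind of case lowers the result slightly.

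**How often it could arise.** The chance of at least one case in 10 is 1 - (1 - p)^10. For an assumed per-patient rate p of 2%, 5%, 10% or 20% this is 18%, 40%, 65% or 89%.

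**The case against.** The strongest reply is that section 14.0 governs participation and not the analysis set. It does not say that removed participants are dropped from a denominator or replaced, and analysis sets are commonly left to a statistical analysis plan, which is not at hand. The sentence about those who leave after imaging mainly explains how their follow-up will be obtained. The cause of each withdrawal is recorded, so with 10 patients at one site no failure is hidden. The rule also has a sensible use: the primary research question in section 2.0 is a before-and-after comparison, and a patient without both acquisitions cannot contribute to it.

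Much of this stands. A reader might infer that the protocol expressly excludes these cases from the feasibility result; it does not. Recording a cause, however, is not the same as counting the case as a failure. The protocol itself fixes the removal rule and says nothing about its main failure event. The paired comparison justifies leaving such a patient out of that comparison, but not out of the feasibility count.

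Three further inferences should not be drawn:

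- That it is unclear what a full acquisition is. Sections 5.3 and 6.0 largely settle it; only a run cut short after the benchmark needs a rule.
- That reverse arthroplasty will produce cases with no repaired tendon to image. Section 3.0 says only that stability does not depend on repair there, not that repair will be omitted.
- That withdrawn participants lose the 1-month collection of serious adverse events. Section 9.0 lists it for all patients, and section 14.0 does not cancel it. In any case this is a separate matter.

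**Conclusion.** The point holds and should be fixed. As written, the fourth ground in section 14.0 removes participants for the kind of event that the primary objective exists to detect, and does not distinguish it from unrelated causes. The conclusion that such cases leave the feasibility result rests on the natural reading of the section, not on an explicit statement.

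Each imaging-process failure left out of 10 hides about 10 percentage points when all other patients show signal. With no such failure there is no effect.

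A reader might infer that a go/no-go decision is biased. The documents do not support that: no threshold or feasibility proportion is set, so what changes is how favourable the reported feasibility looks. Nor are all failures lost, because completed imaging without signal does not meet the fourth ground and still counts.

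**What to change.** Amend the fourth ground in section 14.0 to say the following:

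- A participant in whom imaging was attempted but not obtained at one or both time points, for a reason related to the imaging process, may stop study imaging and be left out of the paired perfusion comparison. That participant stays in the feasibility denominator as a failure, reported by the recorded cause.
- An acquisition cut short after the section 4.0 benchmark was captured is judged on that benchmark.
- Unrelated causes (tendon tear, consent withdrawn, surgery cancelled) are reported separately and not as imaging failures.

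The cost is a few sentences by protocol amendment, using causes that section 14.0 already requires to be recorded. No patients or procedures are added. The downside is that the reported feasibility may be less favourable.

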15.0 Risks to Subjects*

The risks to subjects are minimal in relation to anticipated benefits and/or knowledge that might reasonably be expected from the results of this clinical trial.

Risk of ICG injection: ICG (Indocyanine Green) will be administered intravenously twice: once before and once after the repair. ICG is FDA approved for human use in angiography for ophthalmology and cardiology applications and is given routinely to patients in these clinical settings. The risks are considered minimal and consist of nausea, vomiting, hives, increased heart rate in subjects with particular sensitivity to the dye. ICG does contain sodium iodide and patients with a history of allergy to iodides will be excluded. Anaphylactic or urticarial reactions are rare but have been reported in patients both with and without a history of allergy to iodides. Anaphylactic deaths have been reported following IGG administration during cardiac catheterization. Reported rates of mild, moderate and severe adverse reactions to ICG are 0.15%, 0.2% and 0.05%. Every effort will be made to minimize this risk as much as possible. It is the standard of care at this institution to obtain information related to allergies, sensitivities and past medical histories upon patient arrival. Patients will also be monitored throughout their hospitalization, as is the standard of care, by everyone involved in their medical care for evidence of new or previously unknown reactions or sensitivities. Additionally, at all times ICG fluorescence imaging assessments are taking place, both surgical and anesthesia staff will monitor patients closely for any adverse reaction to ICG. Surgical and anesthesia staff will also monitor patients for at least 30 minutes after all ICG fluorescence assessment procedures have been completed. In the event of an unexpected allergic reaction, Dartmouth-Hitchcock Medical Center and all affiliated groups within this institution have procedures in place for managing patients with unknown or unexpected allergic reactions. If such a reaction were to occur, all standard of care treatments will be provided including but not limited to treatment with appropriate agents

PROTOCOL TITLE: Pilot feasibility study of dynamic contrast-enhanced fluorescence imaging to guide total shoulder arthroplasty approach

such as epinephrine, antihistamines and corticosteroids. Risk of infection from IV injection is also extremely rare but can occur. Pregnant women are excluded from the study. A pregnancy test is administered to women of child-bearing age.

Prolonged operating room time: Because the ICG fluorescence assessments will take place in the operating room, participation in this study may increase the amount of time spent under surgical anesthesia in the operating room. For the average case, an additional 10 minutes at most will be incurred. However, the research staff will make every effort to minimize this risk by performing the assessment test while other required operative procedures are being performed.

Risk of confidentiality breach: As with any protected health information, loss of privacy may lead to problems with insurability or social stigmatization. The risk to subjects is low and members of the research team will make every effort to ensure that information is kept private and protected to the fullest extent possible. Any and all information will be stored and managed in a secure manner, following all applicable federal regulations and guidelines and according to institutional policies and practices. Any electronic information collected will be stored on password protected, HIPAA compliant computers maintained in private, locked offices within secure areas of Dartmouth-Hitchcock Medical Center with limited access. Any non-electronic records collected will be stored likewise, as well. Any discussions between patients and the research staff will be conducted in a private location.

Information about study subjects will be kept confidential and managed according to the requirements of the Health Insurance Portability and Accountability Act of 1996 (HIPAA). Risk of breach of confidentiality of the medical records and status of participants will be minimized. Databases which are used to store subject-sensitive information are password-protected and encrypted during file/data transfers from viewing terminals. Access will be limited to research team members who have undergone CPHS training at Dartmouth. Whenever possible and practical standard-of-care clinical data used in the research will be de-identified when under analysis.

16.0 Potential Benefits to Subjects*

Patients enrolling in this study will not benefit directly because no diagnostic or therapeutic decisions will occur based on the study, and thus, administration of the study is not intended to alter the surgical procedure. However, future patients may benefit from the knowledge gained from the study since this study may provide an objective, intraoperative, and real-time methodology to assess subscapularis tendon perfusion and potential for correlation to outcomes.

17.0 Data Management* and Confidentiality

Data Confidentiality:

PROTOCOL TITLE: Pilot feasibility study of dynamic contrast-enhanced fluorescence imaging to guide total shoulder arthroplasty approach

The use of PHI is necessary for the purposes of this research and the PI and investigational team will protect the confidentiality of the subjects through the following actions:

Patients will be assigned a unique study identifier (*study ID*) based on the order in which they are recruited and a list of study IDs and the patients they correspond to (PHI) will be kept on a Dartmouth-Hitchcock secure server accessed by a DH laptop (the “H:/” drive). This is the only ‘key’ to matching patients and their corresponding study ID, and is only used to retrieve patient outcomes for the data analysis, and in the unlikely event that there is a reported adverse effect, to investigate the event.

A secured DH laptop will also store, in a separate document, a table containing the study date and anonymous study ID will be listed, along with any outcome information as it becomes available. This file will be kept separate from the *file containing the study ID keys*, to minimize the chance it will be *inadvertently shared with unauthorized individuals*.

The file containing the study IDs and which patients they correspond to (ID Key), will be destroyed once all outcomes have been recorded and/or the follow-up period has passed, *unless required* by the sponsor to maintain the information for an extended period of time. In that case, the ID Key will be destroyed at the earliest opportunity consistent with federal regulations.

Protected health information will not be reused or disclosed to any other person or entity, except as required by law, for authorized oversight of the research study, or for other research for which the use or disclosure of protected health information for which an authorization or opportunity to agree or object is not required by 45 CFR 164.512.

18.0 Provisions to Monitor the Data to Ensure the Safety of Subjects*

Since the PDD device does not meet the exempt criteria for an IDE, we request an abbreviated IDE determination from the IRB. [name] will serve as an independent research monitor for this study. He has expertise consonant with the nature of the risks identified within the research protocol and meets all of the following criteria:

- a) Is independent of the team conducting the research involving human subjects.
- b) Can stop the research, remove individual subjects, and take steps to protect subjects until the IRB assesses the monitor’s report.

PROTOCOL TITLE: Pilot feasibility study of dynamic contrast-enhanced fluorescence imaging to guide total shoulder arthroplasty approach

- c) Will promptly report observations and findings to the IRB or other designated official.
- d) Has an IRB approved written summary of duties, authorities, and responsibilities based on specific risks or concerns about the research.
- e) Has confirmed in writing his/her duties, authorities, and responsibilities

With regards to patient safety, ICG will be administered by an anesthetist in the operating room while they are being continuously monitored per anesthesia standard of care. Post-operatively, they are transferred to the Post-Anesthesia Care Unit (PACU) where they are monitored continuously by nursing staff supervised by anesthesiologists. During this entire time vital signs (including temperature, pulse, respiratory rate and blood pressure) are collected as standard of care. All clinical data will be reviewed for adverse events for a period of 30 minutes post-injection.

Day of surgery Procedures	Pre-Infusion	0-30 minutes post-infusion
Pulse	X	X
Blood Pressure	X	X
Temperature	X	X
Respiratory Rate	X	X
Adverse Events		X

With regards to data monitoring, the program manager at D-H will be responsible for ensuring that all patient data is complete. This will be monitored on a week-by-week basis and appropriate clinicians and/or research coordinators will be queried to complete incomplete patient data.

